The study will be conducted both in the laboratory and in the naturalistic environment with a multiethnic sample of 211 adult community participants from upper Manhattan who do not have a history of *CVD, diabetes, chronic kidney disease, difficulty with blood draws,* or another *major medical condition* and are not taking antihypertensive medication. During a Laboratory Visit, urinary sodium excretion in response to mental stress tasks will be examined. Urinary volume, electrolytes, creatinine, and endothelin-1 will be measured at baseline, post-stress, and recovery; salivary cortisol will be measured at baseline and post-recovery; the urinary albumin-to-creatinine ratio will be measured at baseline; plasma angiotensin II and epinephrine/norepinephrine will be measured at baseline and post-stress, and a basic metabolic panel, a lipid panel, and a Hemoglobin A1c assessment will be used at the baseline only. Blood pressure and heart rate will be measured continually during the Laboratory Visit (every five minutes) and for the following 24 hours (every 30 minutes).

In the naturalistic environment, during the 24-hour period following the Laboratory Visit, the diurnal pattern of sodium excretion (measured during the daytime and nighttime) will be assessed by measuring urine volume and the urine concentrations of electrolytes and creatinine. Heart rate will be monitored using ABPM and ecological momentary assessments (EMA) of perceived stress will be surveyed.

The study has high clinical significance for improving our understanding of how psychological stress, sodium excretion and its *diurnal* pattern, and the *diurnal* pattern of BP are linked, and has the potential for identifying a treatment target to reduce the CVD risk associated with reduced BP dipping.

3. Study Procedures

a. Participant Engagement

Interested individuals will review an online information sheet and provide consent to participate in an electronic eligibility screen. This form will provide the contact information of the primary investigator, clinical research coordinator, and IRB office to ensure that all questions about the study, form, and participant's rights are answered before consent for screening is provided. Consent must be provided before access to the eligibility screen is allowed.

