Next, the participant will drink about one cup of bottled spring water. During the next 10 minutes, a research assistant (separate from the research coordinator) known as the stress inducer will read a mental stress script and conduct two stress tests. First, the participant will be shown a series of words for five minutes and a research coordinator will ask him/her to name the color of each (Stroop Color-Word Conflict Task). Then, for another five minutes, the participant will be asked to complete a mental arithmetic task, comprising of a series of subtractions and additions (Mental Arithmetic Task). The stress inducer will adjust the difficulty of the task appropriate for each participant. The stress inducer will ask the participant to work as quickly and accurately as possible for both tasks.

Immediately after the math task, the participant will be asked about the level of stress he/she is feeling using a VAS measurement. Then, the participant will use the bathroom, where he/she will be asked to urinate into a collection container. He/she will return to the exam room chair and another blood sample of about 24.5 milliliters, or 5.5 teaspoons, will be drawn. If the phlebotomist is not available to draw the participant's blood within the exam room, participants will be escorted to the phlebotomist within the CTSA for this service.

Next, the participant will drink about one cup of bottled spring water and remain inactive during for a post-stress recovery period. During this time, participants will rest naturally, allowing for elevated heart rate, increased blood pressure, and other stress symptoms to recover. Twenty minutes following the end of the stress induction, a saliva sample will be collected. After 30 minutes of recovery, the participant will be asked about the level of stress he/she is feeling for a final time, using a VAS measurement. Then, he/she will use the bathroom and asked to urinate into a collection container one final time.

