Before leaving the Laboratory Visit, the participant's non-dominant arm will be fitted with a new standard ambulatory blood pressure monitor (ABPM). A research coordinator will explain how to use the device, provide one detailed instruction sheet and one concise instruction sheet, and provide a paper form where the times at which participants fall asleep, wake up, take naps, and remove the device may be listed. Participants will also receive a cooler containing two urine collection bottles, which are to be used following the Laboratory Visit. The participant will also receive instructions on the two bottles for collecting daytime and nighttime urine, respectively, over the next 24 hours. One, labelled Day, should be used during the day following the Laboratory Visit. The other, labelled Night, should be used if the participant wakes up to urinate during the night and for the first instance of urination after waking up the next day. The participant will be instructed to continue their normal daily and nightly routines, but they must limit their alcohol intake to one drink during the 24 hour period. The Laboratory Visit may take up to 3 hours.

The clinical research coordinator will ensure that, at 5 random times throughout the day and evening, the participant will be prompted by text message to respond electronically to 5 short questions through Qualtrics. The questions will ask about how participants feel in that moment.

After 24 hours, participants will return the ABPM device, the cooler containing both urine collection bottles, and the cooler containing any remaining food from the diet to [name] Hypertension Lab (BB-210 or Tower 1). They will complete a final 5-question survey through Qualtrics, identical to the ones they received via text that will ask them about the emotions they were feeling that morning prior to the visit. Participants will be provided the option of having Lyft concierge rides coordinated for them while traveling with the cooler, our research team will coordinate this service. Alternatively, transportation may be provided at the discretion of the Principal Investigator on a case-by-case basis. Patient satisfaction surveys will be provided at this time if participants are interested in completing one.

b. Blood, Urine, and Saliva Analysis

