Primary Aim 1: Standard regression analysis will be used. We will estimate the unadjusted relation of awake-to-sleep ratio of urinary sodium excretion rate to change in urinary sodium excretion rate with stress. Next, we have a priori selected the following covariates for adjustment in a multiple regression model: age, sex, race/ethnicity (non-Hispanic whites, non-Hispanic blacks, Hispanics, and other), and body mass index. Age, sex, and race/ethnicity are standard covariates in studies of hypertension given their well-known associations with BP. Body mass index is included as a covariate since it is associated with both lower stress-induced sodium excretion and lower day-to-night ratio of urinary sodium excretion rate. The statistical significance of the coefficient for the change in urinary sodium excretion rate with stress in this adjusted model will constitute the primary test of the hypothesis. Sensitivity analyses will be performed to assess whether the strength of the association changes when additional covariates are included. Higher clinic SBP/DBP and parental history of hypertension are associated with lower stress-induced sodium excretion. Fasting blood glucose and 24-hour creatinine clearance are associated with lower daytime-to-nighttime ratio of urinary sodium excretion rate. Each of these will be evaluated as candidate covariates by selecting those that are associated with the outcome (awake-tosleep ratio of urinary sodium excretion rate) at p<0.10. Finally, secondary analyses will use generalized additive models (GAM) to explore potential non-linearity of the relationship, using PROC GAM in SAS.

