Primary Aim 2: The same approach for Hypothesis 1 will be used for the analysis of this hypothesis. SBP dipping and DBP dipping will be the primary and secondary outcomes, respectively. The *a priori* covariates that will be included in adjusted models are: age, sex, race/ethnicity, body mass index, 24-hour sodium excretion, 24-hour potassium excretion, 24-hour creatinine clearance, FENa, current smoking, alcohol consumption, and fasting blood glucose. In addition to age, sex, and race/ethnicity (which were chosen because they are standard covariates in hypertension studies), the other measures were chosen as covariates as they may confound the association between the *diurnal* pattern of sodium excretion and the *diurnal* pattern of BP. Sensitivity analyses will be performed after additional covariates are included in the adjusted model. Prior studies have suggested that physical activity and fasting glucose are associated with the diurnal pattern of BP. Each of these measures will be evaluated as candidate covariates using the same approach described above for Primary Aim 1.

Sample Size and Minimum Detectable Effect Sizes for Primary Aims: The sample size for this study was selected to ensure 80% power to detect a bivariate/partial correlation between the primary predictor and outcome of r=0.20 or greater; this is conservative, but consistent with our preliminary data in which the correlation between the change in urinary sodium excretion rate with stress and awake-to-sleep

ratio of urinary sodium excretion rate (Primary Aim 1) was 0.25, and the correlation of awake-to-sleep ratio of urinary sodium excretion rate and SBP dipping (Primary Aim 2) was 0.30. The minimum sample size required to detect this effect size with power 80% is 194 with valid data for the three primary measures (change in urinary sodium excretion rate with stress, awake-to-sleep ratio of urinary sodium excretion, and SBP dipping). We are targeting a final minimum sample size with complete data of 200.

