In secondary analyses, we also examined whether the association between urinary sodium excretion rate with stress in the laboratory and awake-to-asleep ratio of urinary sodium excretion over a 24-hour period was modified by EMA ratings of perceived stress. Controlling for each EMA rating and change in urinary sodium excretion rate with stress, we tested their multiplicative interaction term in a fully adjusted model. A positive interaction effect would suggest that the association between urinary sodium excretion rate with stress in the laboratory and awake-to-asleep ratio of urinary sodium excretion over a 24-hour period is stronger among those who experience higher stress during the awake period of monitoring. The analyses were repeated for each EMA rating of negative affect.

A p value of <0.05 was considered statistically significant.

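### The Day urine and awake blood pressure windows open about half an hour after the stress tasks, so carry-over into the Aim 1 ratio (and, slightly, Aim 2 dipping) is possible and is not examined

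*Protocol*

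**What the plan says.** Protocol section 2 (Study Design) places the diurnal measurements directly after the session: "In the naturalistic environment, during the 24-hour period following the Laboratory Visit". Section 3a (Participant Engagement) gives the order of events. The two stress tasks take 10 minutes and are followed by a stress rating, a void and a blood draw. Then: "Next, the participant will drink about one cup of bottled spring water and remain inactive during for a post-stress recovery period". After 30 minutes there is a last rating and a separately collected recovery void. The ambulatory monitor is then fitted and two bottles are issued. Of these, "One, labelled Day, should be used during the day following the Laboratory Visit"; the other is for the night and the first void after waking.

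Sodium and volume are assayed at baseline, post-stress and recovery (sections 2 and 3b). Day urine is one pooled sample.

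In section 4, the Aim 1 outcome is the awake-to-sleep sodium ratio and the predictor is the change in sodium rate with stress. The primary test is "The statistical significance of the coefficient for the change in urinary sodium excretion rate with stress in this adjusted model". Aim 2 relates the same ratio to systolic dipping (primary) and diastolic dipping (secondary). No analysis in the protocol or the SAP names the recovery urine, checks return to baseline, or sets aside early ambulatory readings.

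**The concern.** Aim 1 treats the awake-to-sleep ratio as the participant's ordinary diurnal pattern and asks whether the laboratory response is associated with it. If part of the provoked sodium excretion is still running when the Day bottle opens, people with a larger laboratory response get a larger ratio for that reason alone. The coefficient would be positive, the hypothesised direction, even if the laboratory response said nothing about ordinary days. None of the Aim 1 covariates (age, sex, race/ethnicity, body mass index) removes this, and the pooled bottle cannot be split afterwards.

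Aim 2 has a weaker form of the same problem: residual sodium excretion would raise the ratio while residual pressure elevation would raise the awake mean, and so dipping. At stake is how far a positive primary result can be read as evidence about the usual diurnal pattern.

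**Working it through.** **1. The plan's own figure.** The protocol asks for "80% power to detect a bivariate/partial correlation between the primary predictor and outcome of r=0.20 or greater", and the SAP says "A p value of <0.05 was considered statistically significant". With Fisher's z and a two-sided 0.05 level:

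n = ((1.960 + 0.842) / atanh(0.20))² + 3 = 193.97, so 194.

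This matches: "The minimum sample size required to detect this effect size with power 80% is 194 with valid data for the three primary measures". (One-sided would give 154.) At the planned size, "We are targeting a final minimum sample size with complete data of 200", power for r = 0.20 is 81%, and an observed r of about 0.14 is already significant.

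**2. Inputs for carry-over.** From the protocol: the window opens 0.5 h after the stress tasks, and ambulatory readings come every 30 minutes. Not in the documents, so assumed:
- Day collection of 11 h.
- q, the SD of the stress change divided by the mean daytime sodium rate: 0.3 to 0.6.
- τ, the mean duration of the response under exponential decay from the end of stress: 0.5 to 2 h.
- s, the SD of the log awake-to-sleep ratio: 0.4.
- True Aim 1 association: zero.

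**3. Formulas.** Share of the response added to the mean Day rate: c = τ(e^(−0.5/τ) − e^(−11.5/τ)) / 11. Induced correlation: r = cq / √(s² + (cq)²). With predictor reliability 0.5 (assumed, because the change is a difference between short collections), multiply r by √0.5 = 0.707. The chance of p<0.05 at n = 200 comes from atanh(r)·√197 against ±1.96.

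**4. Results.**

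| q | τ (h) | c | r | chance of p<0.05 | r, reliability 0.5 | chance of p<0.05 |
|---|---|---|---|---|---|---|
| 0.3 | 0.5 | 0.017 | 0.01 | 5% | 0.01 | 5% |
| 0.3 | 1 | 0.055 | 0.04 | 9% | 0.03 | 7% |
| 0.6 | 1 | 0.055 | 0.08 | 21% | 0.06 | 13% |
| 0.6 | 2 | 0.141 | 0.21 | 84% | 0.15 | 54% |

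Last row: cq = 0.141 × 0.6 = 0.085, and r = 0.085 / √(0.16 + 0.0072) = 0.21.

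**5. What r = 0.20 would need.** cq = 0.20 × 0.4 / √0.96 = 0.082. That takes τ of about 1.9 h at q = 0.6, or about 3.6 h at q = 0.3. A variant with an 11.5 h Day window and s of 0.4 to 0.6 needs a half-life of 1.6 to 2.3 h at q = 0.5, 3.2 to 5.4 h at q = 0.25, and 0.9 to 1.3 h at q = 1.0. In that variant, half-lives of 15 to 30 minutes give r of at most 0.08.

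**6. Aim 2.** Assume a residual systolic SD of 5 mmHg in the first 2 hours (4 of about 22 awake readings), a dipping SD of 8 mmHg, and residual pressure perfectly correlated with residual sodium. The pressure loading is (5 × 4/22) / 8 = 0.11. Multiplied by the sodium loadings of 0.01 to 0.21 in step 4, the induced r is at most 0.11 × 0.21 = 0.02.

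**The case against.** The plan has a separation step. A void follows the tasks, the recovery period is there to let stress effects settle, and a further void precedes the Day bottle. If the bladder is emptied, urine made during stress and recovery stays out of the outcome. This stands: the washout is short, not absent. If nothing decayed during recovery, the four scenarios would give r of about 0.03, 0.07, 0.14 and 0.26; that ignores the recovery period.

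The documents give no time course, so carry-over is a possibility and not a finding. This also stands. Nor is the direction certain. Sodium lost in the laboratory lies outside the Day bottle, and with dietary sodium held fixed a larger loss could lower later Day excretion and work against the hypothesis.

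A reader might infer that awake blood pressure helps to create the Aim 1 association. It cannot, because the Aim 1 outcome contains no blood pressure. A reader might also infer that carry-over is enough by itself to produce the Aim 1 result. The documents do not support that: on the assumed inputs it takes a large response that lasts for hours after a 10-minute stressor.

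Finally, neither document defines which samples form the change with stress, so it cannot be excluded that recovery urine is part of the predictor. Even so, no check on return to baseline is planned.

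**Conclusion.** The point holds as a gap in the analysis plan, not as a demonstrated bias. Both outcome windows open on the stress day after a 30-minute recovery and a separate void, and nothing planned tests whether provoked excretion has ended by then. With no true association, the induced Aim 1 correlation is about 0.01 to 0.21, or 0.01 to 0.15 with predictor reliability of 0.5, and zero if excretion is back to baseline at the recovery void. Only the corner with the largest and longest response reaches the design target of 0.20, although smaller values still raise the false-positive rate above 5%. Compensation could push the other way. For Aim 2 the effect is about 0.02 at most on the stated assumptions. Response size, duration, Day length, reliability and all SDs are assumptions. The sample size of 194 is unaffected. Label: cheap improvement.

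**What to change.** All three changes use data already collected and leave the primary models as they are.

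1. State which samples form the change with stress. Report the recovery-minus-baseline sodium excretion rate and its correlation with that change. Add an Aim 1 sensitivity model with recovery-minus-baseline rate as a covariate, labelled as a sensitivity analysis because it may over-adjust: recovery excretion is itself part of the stress response.
2. Repeat the Aim 2 dipping models without ambulatory readings from the first 2 hours after the visit (2 h at one per 30 minutes, about 4 readings).
3. State same-day collection as a limitation on reading the ratio as the usual diurnal pattern.

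The cost is SAP wording and slightly less precision in the sensitivity models.

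Two other remedies are not worth adopting. Restricting Aim 1 to participants whose recovery rate is within 10% of baseline selects on a post-stress variable. With an assumed 25% measurement CV per sample and no carry-over at all, the difference has an SD of 0.25 × √2 = 0.354, so about 22% would qualify (about 45 of 200), with about 26% power at r = 0.20. A separate early-afternoon bottle adds a procedure, may be moot because the SAP is written in the past tense, and would mix two definitions of the awake rate.

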the participant may have. A HIPAA Authorization form will also be provided to the participant. The provision of consent on both forms is necessary for further study participation. If consent is provided, demographic information will also be collected at this time. Participants will also be asked to provide a home address so coordinators can provide an estimation of transportation costs that can be reimbursed in future visits. Then, the clinical research coordinator will measure participant blood pressure three times with one-minute intervals between measurements. Measurements will be made using an Omron HEM-907XL device. These measurements will be used to ensure that participants are not in violation of the study's eligibility criteria concerning hypertension. The coordinator will also ensure that participants have readily available veins for blood draws during the Laboratory Visit. A copy of blood pressure readings will be provided to participants. Next, the "ISQ: Psychometric Evaluation" will be administered as a short survey to ensure that participants do not experience insomnia, another condition precluding participation in the study. If the participant does not meet eligibility criteria for either blood pressure or insomnia, then the participant is compensated and the visit will end.

If the participant remains eligible, then the "Life Events Checklist" and "PTSD Checklist" will be provided separate from the other measures to ensure that the completion of these two questionnaires does not alter stress felt during the Laboratory Visit. Stress- and demographic-related measures will be presented to participants using Qualtrics opened on a provided laptop, and the insomnia survey will be administered as a paper form. The participant's weight, height, hip and waist circumference, gender, age, normal activity levels, and dietary limitations will then be recorded on a Bionutrition Center form. In addition, a list of foods provided by the Bionutrition Center will be provided and the participant asked whether they agree to eat all of the foods on the checklist. This information will be recorded for research use and forwarded to the Bionutrition Center to prepare the meals and snacks that will be consumed in the three days prior to the Laboratory Visit.

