confirm the dates that were proposed at the Enrollment Visit. Additionally, the clinical research coordinator will make the necessary preparations for these visits, including informing the Bionutrition Center about the need for prepared meals, scheduling an examination room in the Irving Institute for Clinical and Translational Research (CTSA), and preparing materials for the visit.

Within eight weeks of the Enrollment Visit, the Pre-Laboratory Visit will occur. At this time, the participant will be provided with meals and snacks prepared by the Irving Institute Bionutrition Unit. These meals will be packed into a portable cooler for participant convenience. In addition, the participant will have been provided with the link to the SABRE Online Measures one week prior to the Pre-Laboratory Visit. The research coordinator will check in with the participant at this time to verify they have completed the questionnaire by this time and respond to any questions that may arise. These measures ask about different aspects of life and personality, and they may be completed at any time before the Pre-Laboratory Visit.

At the end of the Pre-Laboratory Visit, participants will be informed that fees associated with parking or transportation to their desired destination with the cooler of food can be reimbursed during the final visit, provided they pay in cash and keep the receipt.

Starting the morning after the Pre-Laboratory Visit, participants will be asked to eat only this specially prepared food for the next 3 days. No additional foods or drinks may be consumed other than water, plain decaf or mint or chamomile tea without sugar, milk or other additives, and up to one cup, or approximately 8 fluid ounces, of black coffee/tea per day. The meals and snacks consumed each day will contain the same total amount of salt. The diet that will be provided to participants is not a dietary intervention designed to lower the amount of sodium in a person's diet, but rather to keep the amount of dietary sodium fixed during the study visits. As such, the amount of dietary sodium (as well as potassium) are considered to be a moderate amount, which is consistent with the average amount a US adult is taking. Please see

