https://www.ars.usda.gov/ARSUserFiles/80400530/pdf/1112/Table 1_NIN_GEN_11.pdf. The participant will eat this food for the three days following the Pre-Laboratory Visit and leading up to the Laboratory Visit. The research assistant will contact him or her every day to make sure there are no issues. The Laboratory Visit will be scheduled 4 days after the Pre-Laboratory Visit. For example, if the Pre-Laboratory Visit takes place on Thursday, the Laboratory Visit will take place on Monday.

For the Laboratory Visit, participants will come to the [name] Hypertension Lab (Tower 1) at the Columbia University Medical Center. Appointments will be scheduled between 8 AM and 9 AM in the morning four days after the Pre-Laboratory Visit. This visit should be attended in a fasting state (without eating or drinking anything more than small sips of water after midnight of the day before. Participants will also be asked to not exercise for 12 hours before the visit and to not smoke within the hour prior to the visit. At 30 minutes before the appointment, the participant will be asked to drink 8 ounces of Poland Spring water that will be provided prior to the appointment.

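### Does the unclear diet rule and the lack of a described meal-time record for the 24-hour collection call for a change to Aim 2?

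*Protocol*

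**What the plan says.** Three statements in Protocol section 3a end the diet at the Laboratory Visit:

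- The kitchen is to "prepare the meals and snacks that will be consumed in the three days prior to the Laboratory Visit".
- From the morning after the Pre-Laboratory Visit, "participants will be asked to eat only this specially prepared food for the next 3 days".
- "The participant will eat this food for the three days following the Pre-Laboratory Visit and leading up to the Laboratory Visit".

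The Protocol's example of the spacing is that "if the Pre-Laboratory Visit takes place on Thursday, the Laboratory Visit will take place on Monday". On the Laboratory Visit itself it says "This visit should be attended in a fasting state".

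Two statements in the same section suggest a longer diet. The purpose of the diet is "rather to keep the amount of dietary sodium fixed during the study visits", and "the cooler containing any remaining food from the diet" comes back only when the 24 hours are over.

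Section 3a also tells participants to keep to their usual routines during the 24 hours and allows one alcoholic drink; alcohol is not among the drinks permitted on the diet. Section 2 describes the setting: "In the naturalistic environment, during the 24-hour period following the Laboratory Visit, the diurnal pattern of sodium excretion" is measured then. The paper form is described as holding sleep, wake, nap and device-removal times, and the text-message questions ask about feelings.

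The Aim 2 covariates in Protocol section 4 and in the SAP include 24-hour sodium and potassium excretion. Neither document lists a variable for the timing of intake.

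**The concern.** The 24-hour collection supplies the Aim 2 predictor (awake-to-sleep sodium ratio) and, through the monitor worn at the same time, the Aim 2 outcome (SBP dipping). A person who eats a salty meal late may excrete more of it at night, which lowers the ratio. If the same meal also reduced dipping by some other route, part of the association would reflect when people ate.

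The planned covariates adjust for how much sodium was excreted over the day, not for when it was eaten. Timing that was not written down cannot be recovered later. Resolving the diet text would not remove the question either, because section 3a equalises only the total salt per day, so timing could vary even if the diet continued through the collection.

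**Working it through.** **1. Timeline, from section 3a.** Pre-Laboratory Visit on Thursday; diet Friday, Saturday and Sunday; fast from midnight; Laboratory Visit on Monday at 8 to 9 AM, lasting up to 3 hours, so it ends by 11 AM to noon. The collection runs from then until Tuesday. On the reading that the diet ends at the visit, 0 of the 24 collection hours fall within it. On the reading suggested by the food return, some or all may. The text supports neither conclusively.

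**2. The plan's own figure.** Section 4 gives 194 participants for 80% power at r = 0.20. With Fisher's z and two-sided alpha 0.05 (sidedness is not stated):

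n = [(1.960 + 0.842) / atanh(0.20)]² + 3 = 193.97, so 194.

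It reproduces. At n = 200 the power is 81.2%, before counting covariates. The diet question does not touch this calculation.

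**3. How far timing alone could move the ratio.** The documents give no inputs, so these are assumptions: 100 mmol excreted awake and 35 mmol asleep, plus a load L of 25 to 75 mmol, with 10 to 20 percentage points of L moving from awake to asleep. Hours awake and asleep cancel in the relative change.

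- Smallest case, L = 25, shares 0.35/0.25 becoming 0.25/0.35: 108.75/41.25 = 2.636 becomes 106.25/43.75 = 2.429, a fall of 7.9%.
- Largest case, L = 75, shares 0.40/0.20 becoming 0.20/0.40: 130/50 = 2.600 becomes 115/65 = 1.769, a fall of 32.0%.

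These are shifts within one person. Without a between-person standard deviation of the ratio, they cannot be turned into a correlation or a bias.

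**4. Shared-cause illustration.** Let late intake correlate a with a lower ratio and b with less dipping, with no other link between ratio and dipping. The induced correlation is ab. The chance of p<0.05 uses n = 200 and the same Fisher z. The last column is the partial correlation left from an observed 0.30, which is (0.30 − a²)/(1 − a²).

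| a = b | Induced r | Chance of p<0.05 | 0.30 becomes |
|---|---|---|---|
| 0.2 | 0.04 | 9% | 0.27 |
| 0.3 | 0.09 | 25% (24.5%) | 0.23 |
| 0.4 | 0.16 | 62% | 0.17 |

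To account for all of the pilot 0.30, a and b would each have to be √0.30 = 0.548. If late intake lowered the ratio but increased dipping, the induced values would be −0.04, −0.09 and −0.16, and the planned estimate would be too small.

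**5. What a last-meal-time check could show.** Let the recorded time correlate c with late sodium. After adjustment the induced slope is ab(1 − c²)/(1 − a²c²). With a = b = 0.3, starting from 0.09:

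- c = 0.5: 0.0675/0.9775 = 0.069, so 23% is removed.
- c = 0.7: 0.0459/0.9559 = 0.048, so 47% is removed.
- c = 0.9: 0.0171/0.9271 = 0.018, so 80% is removed.

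If instead late sodium acts only through the ratio, the coefficient does not change in expectation. Its standard error grows by 1/√(1 − a²c²): from 1.005 (a = 0.2, c = 0.5) to 1.072 (a = 0.4, c = 0.9), so about 0.5% to 7%.

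**The case for a change.** The strongest case for a change is this. The diet text cannot be read one way. Section 1 itself says that sodium intake raises blood pressure and so excretion. Section 4 and the SAP choose covariates because they may confound this very association. At the upper assumed correlations, an Aim 2 test with no direct link would reach p<0.05 in up to 62% of trials, against a nominal 5%. A few added lines on a form and one extra model would cost little.

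Part of this stands. The passages on the diet do need to be reconciled, no record of intake timing is described, and 24-hour totals do not stand in for timing.

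The rest is weaker. Section 1 states the link from intake to blood pressure for the daytime. For the night it ties blood pressure to sodium excretion, which is the pathway Aim 2 sets out to examine. Salt eaten in the evening while awake could raise awake pressure and so increase dipping, so the direction of any distortion is not known. The 62% rests on assumed correlations of 0.4 on both sides with the unfavourable sign.

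Section 2 puts the collection in the naturalistic environment, where meal timing is part of the natural variation in the exposure. Adjusting for it could remove real signal. Section 4 admits additional Aim 2 covariates only if they are associated with the outcome at p<0.10, so an unconditional comparison with and without meal time would be a new analysis, not one already planned. The form and instruction sheets are not in the documents, so a record may exist there.

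**Conclusion.** No change to the plan follows. Two separate things are involved.

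The first is a gap in wording. The section 3a statements on the diet should be brought into agreement so that readers know what was eaten during the collection. The study team knows which rule was in force, and stating it alters no endpoint, model or sample size. The documents do not show which reading is right, and this review does not choose one.

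The second is a request for an extra variable and an extra model. Statisticians could reasonably differ on this. The primary model would stay as it is, no bias has been shown, and the check would not be decisive: an unchanged coefficient would not exclude a shared effect, because the proxy may capture as little as 23% of it, and a changed one might reflect lost exposure variation. For assumed same-direction correlations of 0.2 to 0.4, the induced r of 0.04 to 0.16 stays below both 0.20 and 0.30, so late intake would not by itself account for either value.

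The SAP is written in the past tense, so collection may already be complete and form changes too late. If no timing record exists, that is an ordinary limitation for the authors to mention with the Aim 2 result. The conclusion rests on the documents supplied, on assumed correlations for which they give no figures, and on Aim 2 being reported as an association, as the Protocol words it.
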